### **3.3.4 Rationale for Biomarker Assessments**

*Diagnostic* biomarker assessments aim to identify a biomarker that predicts response to GDC0853, which would be valuable to patients and treating physicians as an aid in identifying patients with increased likelihood to achieve clinical benefit, thus guiding treatment decisions. *In addition, at various timepoints after treatment, pharmacodynamic* biomarker samples will be collected and used to advance the understanding of the mechanism of action of GDC-0853 and define PK/PD relationships in SLE patients aiding in dose evaluation in this study as well as dose-regimen selection for future studies (see [Appendix 2](#)).

### **3.3.5 Rationale for PK Sample Collection Schedule**

PK results will be used to perform robust exposure-response and exposure-safety analyses, which will help to characterize how safety and efficacy are impacted by drug exposure and, thus, inform appropriate doses and regimens for future studies of GDC-0853. The PK sampling schedule is designed to capture data at several points during the study in order to *enable the estimation of systemic GDC-0853 exposures and subsequent* exposure-response evaluations and dose-regimen selection for future studies (see [Appendix 2](#)), *which may be reported separately*.

### **3.3.6 Rationale for Other Study Design Elements**

#### **3.3.6.1 Pre-Enrollment Adjudication**

Enrollment into this trial is subject to adjudication by the Sponsor's Medical Monitor or medically qualified designee. The objective of the adjudication process is to ensure that eligibility is based on objectively ascertained, well-documented, and clinically important disease activity. The scope and detailed procedures for the adjudication process are described in [Appendix 3](#).

#### **3.3.6.2 Efficacy Measurements**

The primary efficacy endpoint in this study is a composite of the Systemic Lupus Erythematosus Responder Index (SRI)-4 at Week 48 (see [Table 1](#)). The SRI-4 response criterion is commonly used in SLE studies, is accepted by health authorities to measure reduction in SLE disease activity, and it is a composite measure that includes the SLE Disease Activity Index (SLEDAI-2K), British Isles Lupus Activity Group (BILAG) 2004, and Physician Global Assessment. SRI responses have been detected at timepoints as early as 12 weeks in prior clinical trials; however, therapeutic benefit is often measured at 24 weeks with maximal benefit seen as late as 48-52 weeks post-treatment intervention ([Burgess and McCormack 2011](#); [Furie et al. 2017](#); [Khamashta et al. 2016](#); [Navarra et al. 2011](#)). SRI-4 alone is the primary efficacy endpoint. Achievement of a low, stable, corticosteroid dose has been added to the SRI-4 in the secondary endpoint in order to minimize the confounding effect of corticosteroids, including inflation of the response rates in the comparator arm that can obscure detection of an efficacy signal. *The BILAG-based Composite Lupus Assessment (BICLA) and the SRI-6 are also secondary endpoints as they provide a meaningful metric of SLE disease activity.*

In addition to the primary and secondary SRI endpoints, SRI 5, 7, and 8 are exploratory efficacy endpoints. Furthermore, several other clinically meaningful and exploratory aspects of SLE disease activity will be evaluated, using the Cutaneous Lupus Erythematosus Disease Area and Severity Index (CLASI), *SLICC/ACR Damage Index*, Physician Global Assessment, SELENA-SLEDAI Flare Index (SFI), 28-joint count, and patient-reported outcome (PRO) measures (i.e., Functional Assessment of Chronic Illness Therapy [FACIT]-Fatigue and Patient Global Assessment). Each of these measures has been well established and validated in previous studies.

### **3.3.6.3 Corticosteroid Taper**

There is a substantial unmet need for effective corticosteroid-sparing treatments for SLE and this study will assess the corticosteroid sparing potential of GDC-0853. Chronic corticosteroid use has many adverse short- and long-term consequences, so reducing corticosteroid doses in patients with SLE will decrease the incidence of short- and long-term co-morbidities and potential adverse events, including in patients in this trial. The Glucocorticoid Toxicity Change Index (GTCI) will be used to determine the potential of GDC-0853 to reduce steroid-induced systemic side effects (see [Appendix 12](#)). In addition, the unrestricted use of corticosteroids in SLE clinical trials can confound safety and efficacy measurements and decrease the ability to detect the biologic activity/efficacy of the experimental drug ([Reddy et al. 2013](#)). Thus, to best determine the safety and efficacy of GDC-0853, corticosteroids should be tapered according to a suggested taper schedule, as tolerated (see [Appendix 4](#)). Furthermore, if a patient requires a corticosteroid burst during the Burst Windows, corticosteroids should be tapered back down to baseline (either the Day 1 dose or lowest stable dose the patient achieves) using the suggested taper schedule. Study patients with disease activity that precludes tapering corticosteroid to the target level will be considered trial defined non-responders for the analysis of secondary and exploratory endpoints that incorporate the requirement for OCS tapering.

### **3.3.6.4 Clinical Outcomes Assessments**

PRO and clinician-reported outcome data will be collected to more fully characterize the clinical profile of GDC-0853. To minimize the confounding of PRO assessments that evaluate pain, any potentially painful procedures (e.g., blood draws) should be performed after the pain assessment.

### **3.3.6.5 Stratification**

Randomization will be stratified by disease activity based on the SLEDAI-2K score, entry dose of OCS, and geographic region obtained at screening.

Levels of baseline disease activity (SLEDAI-2K score) and corticosteroid use as well as geographic region independently impact a patient's ability to achieve response on the primary efficacy endpoint. Specifically, a reduction of  $\geq 4$  points in the SLEDAI-2K must be achieved to be classified as a responder. In addition, use of corticosteroids in SLE clinical trials can confound efficacy measurements and decrease the ability to detect the

biologic activity/efficacy of the experimental drug. For this reason, it is important to prevent treatment imbalances in these factors at baseline and thus randomization will be stratified by both SLEDAI-2K score ( $\geq 10$  or  $< 10$ ) and baseline corticosteroid use. Geographic region was chosen as the third strata, because regional variations in the management of SLE can manifest as variability in response rates, including differences in placebo rates (Kalunian et al. 2016; Khamashta et al. 2016). The stratification is intended to balance the proportion of patients from different regions across the study arms in order to limit any confounding of the study results.

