#### **4.1.1 Inclusion Criteria**

Patients must meet all of the following criteria for study entry:

- Signed Informed Consent Form
- Age 18–75 years, inclusive
- Able to comply with the study protocol
- Fulfillment of SLE classification criteria according to either the current American College of Rheumatology (ACR) or Systemic Lupus International Collaborating Clinics (SLICC) criteria at any time prior to or at screening (see Appendix 5 and Appendix 6, respectively)
- At least one serologic marker of SLE at screening as follows:
  - Positive antinuclear antibody (ANA) test by immunofluorescent assay with titer  $\geq 1:80$ ; OR
  - Positive anti-double-stranded DNA (anti-dsDNA) antibodies; OR

- Positive anti-Smith antibody
- At both screening and Day 1, moderate to severe active SLE, defined as meeting all of the following unless indicated otherwise:
  - SLEDAI-2K score  $\geq 8$  (at screening only) with clinical SLEDAI-2K score  $\geq 4.0$  (at both screening and Day 1) (see [Appendix 10](#))
  - Physician’s Global Assessment  $\geq 1.0$  (out of 3) (see [Appendix 15](#))
  - Currently receiving at least one standard oral treatment (*e.g.*, corticosteroids, anti-malarials, and/or immunosuppressants) for SLE within the dose ranges, as specified below (see [Appendix 18](#)):
    - If on an OCS, the dose must be  $\leq 40$  mg/day prednisone (or equivalent, see [Appendix 18](#)) and must have been stable for at least 2 weeks prior to screening as well as during screening
    - If on anti-malarial or *immunosuppressant* therapies, may only be receiving medications from the following list within the specified dose range; dose and route of administration must be stable for 8 weeks prior to screening as well as during screening:
      - Azathioprine: 1 to 2.5 mg/kg/day
      - Methotrexate: 7.5 to 25 mg/week
      - Mycophenolate mofetil: 500 to 3000 mg/day
      - Mycophenolic sodium: 360 to 2160 mg/day
      - Hydroxychloroquine: 200 to 400 mg/day
      - Chloroquine: 100 to 250 mg/day
      - Quinacrine: 100 to 200 mg/day
      - Other: Consult with Medical Monitor

Note: Any combination of azathioprine, methotrexate, mycophenolate mofetil, or mycophenolic sodium is prohibited.

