#### **4.5.8.9 Systemic Lupus Erythematosus Responder Index**

The SRI is a categorical assessment that evaluates disease activity in SLE based on the different organ systems. This index utilizes a combined evaluation of the SLEDAI-2K, BILAG, and Physician Global Assessment to measure response to treatment (see Sections [4.5.8.2](#), [4.5.8.1](#); [4.5.8.7](#)). The SRI-4 primary endpoint defines response as meeting all of the following criteria at Week 48 compared with baseline:

- $\geq 4$  point reduction in SLEDAI-2K score
- No new BILAG A organ domain score or 2 new BILAG B organ domain scores
- No worsening (worsening defined as a  $> 0.3$  point increase) in the Physician’s Global Assessment.

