### 6.4.1 Primary Efficacy Endpoint

The primary efficacy *endpoint* for this study is SRI-4 response at Week 48.

*The primary endpoint will be compared between each of the two GDC-0853 arms and the placebo arm by using the Cochran-Mantel-Haenszel test statistic, stratified by the factors used at randomization. The absolute difference in remission rates and 95% CI for the point estimate will be provided.*

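### The SRI analyses adjust for disease activity only through the screening SLEDAI-2K split at 10, although response is counted from a Day 1 score that is already collected: a small, cheaply avoided loss of precision

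*Combined protocol and SAP*

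**What the plan says.** Protocol section 3.3.6.5 fixes the factors and when they are measured: "Randomization will be stratified by disease activity based on the SLEDAI-2K score, entry dose of OCS, and geographic region obtained at screening". SLEDAI-2K has two levels, 10 or more against less than 10. The reason given is that disease activity at baseline has an independent effect on response, because a drop of at least 4 points is required, so that "it is important to prevent treatment imbalances in these factors at baseline and thus randomization will be stratified by both SLEDAI-2K score".

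Section 6.4.1 compares each dose with placebo "by using the Cochran-Mantel-Haenszel test statistic, stratified by the factors used at randomization". Section 6.4.2 analyses the secondary endpoints, including SRI-4 at Week 24 and SRI-6 at Weeks 24 and 48, in the same way.

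The reference point is set in section 4.5.8.9: "The SRI-4 primary endpoint defines response as meeting all of the following criteria at Week 48 compared with baseline". Section 4.5 identifies baseline with Day 1. Section 4.5.8.2 and Appendix 1 have SLEDAI-2K scored at screening, on Day 1 and at each later clinic visit.

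Under section 4.1.1 the total score must be at least 8 at screening only, while the clinical score must be at least 4 at both screening and Day 1. Screening may fall up to 35 days before dosing and can be extended.

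**The concern.** The protocol's reasoning is about the baseline value, but its adjustment uses an earlier, two-level stand-in. Under the current entry rule the lower stratum holds screening totals of 8 and 9, and the upper stratum pools everything from 10 up. On Day 1 only the clinical score is checked again, so a Day 1 total can be as low as 4. Such a patient meets the SLEDAI-2K criterion only by reaching zero. If SRI-6 means a 6-point drop, by analogy with SRI-4 (the documents do not define it), a patient with a Day 1 total of 4 or 5 cannot respond in any arm. The screening split cannot identify these patients.

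What is at stake is precision. Chance differences between arms in the Day 1 score, within the screening strata, add noise to the estimated difference in response rates. That noise could be removed with data the trial already has. The stated purpose in section 6.1 is estimation and hypothesis generation, so the width of the interval matters.

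**Working it through.** **1. The plan's own power.** Inputs from section 6.1: 80 per arm, 50% against 75%, two-sided 0.05. Enumerating both binomial distributions and summing the probability of tables with p ≤ 0.05:

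- Fisher's exact test: 88.3%, which reproduces the stated 88%.
- Chi-square without continuity correction: 91.1% (normal approximation 91.2%).
- Subgroup, 40 per arm at 0.20, Fisher: 80.1%, against the stated 80%.

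The stated power therefore uses no covariate adjustment. The uncorrected tests below start from about 91%, not 88%.

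**2. Precision of the risk difference.** For a covariate Z and 160 patients in two arms, the large-sample variance is

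V(Z)/160, with V(Z) = 2[p0(1−p0) + p1(1−p1)] − Var{E(Y|Z, placebo) + E(Y|Z, active)}.

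With no covariate, V = 2(0.25 + 0.1875) = 0.875 and SE = √(0.875/160) = 0.0740.

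The documents give no prognostic strength and no screening-to-Day 1 correlation, so both are assumptions. With an odds ratio of 2.0 per SD of the Day 1 score, a correlation of 0.8 and the screening cut at the median (also assumed):

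- The screening split removes 3.6%: V = 0.875 × 0.964 = 0.8435, SE 0.0726.
- The continuous Day 1 score removes 8.8%: V = 0.875 × 0.912 = 0.798, SE 0.0706.
- Equivalent size: 80 × 0.8435/0.798, about 84.5 per arm.
- Chance shift left in by the split: √(0.0726² − 0.0706²) = 0.017, so an SD of about 1.7 percentage points in the estimated difference.

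**3. Power over a range of assumptions.** 6,000 simulated trials per row, 80 per arm. The log-odds of response are linear in the Day 1 score and calibrated to 50% and 75% overall. Randomisation is blocked within the screening split. CMH on the split is compared with a logistic score test adjusting for the continuous Day 1 score.

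| Odds ratio per SD | Correlation | CMH on split | Day 1 adjusted | Gain (points) | Equivalent n per arm |
|---|---|---|---|---|---|
| 1.0 | 0.6-0.95 | 90.3-91.2% | 90.6-91.3% | 0.1-0.3 | 80.0 |
| 1.5 | 0.6 | 91.3% | 92.1% | 0.8 | 82.1 |
| 1.5 | 0.8 | 91.6% | 92.2% | 0.6 | 81.6 |
| 1.5 | 0.95 | 91.3% | 91.9% | 0.6 | 81.2 |
| 2.0 | 0.6 | 91.8% | 93.3% | 1.5 | 85.9 |
| 2.0 | 0.8 | 91.8% | 93.3% | 1.5 | 84.5 |
| 2.0 | 0.95 | 92.0% | 93.1% | 1.1 | 83.2 |
| 3.0 | 0.6 | 92.4% | 95.7% | 3.3 | 93.5 |
| 3.0 | 0.8 | 93.4% | 95.7% | 2.3 | 90.2 |
| 3.0 | 0.95 | 94.2% | 95.7% | 1.5 | 86.9 |

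Keeping the split in the model beside the Day 1 score moves any power figure by at most 0.1 point, which takes the first gain at 1.5 from 0.8 to 0.9. The 0.1-0.3 points at an odds ratio of 1.0 come from changing the test statistic and from simulation error, since the equivalent n stays at 80.0. Type I error was 4.3-5.6% across both methods.

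**4. Check with full stratification.** A separate run used 12 strata (3 regions × 2 OCS levels × 2 SLEDAI-2K levels; three regions is an assumption), 4,000 trials per setting and correlation 0.8. For log-odds slopes of 0.3, 0.5 and 0.7 per SD (odds ratios 1.35, 1.65 and 2.01), power went from 91.9 to 92.5%, 91.7 to 92.6% and 91.8 to 93.3%. The gains of 0.6, 0.9 and 1.5 points agree with the table.

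**The case against.** Analysing by the randomisation strata is standard. The stratified CMH test is valid, and the 95% CI already reflects random Day 1 imbalance. In a hypothesis-generating Phase II study, about one power point is unlikely to change a decision. All of that stands, and it limits the point to a supportive analysis.

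Section 6 defers method details to a Data Analysis Plan that is not among the documents, and section 6.4 allows sensitivity analyses there. A Day 1 model may therefore exist. All that can be said is that the protocol specifies none; the sensitivity analyses it gives as examples are alternative populations.

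A Day 1 total of 4 is an extreme case. The patient must have scored at least 8 at screening, SLEDAI-2K looks back 28 days, and SLE treatment must be stable through screening. How often it happens is unknown, and the sizes above do not depend on it.

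A reader might infer that the Day 1 score is a strong predictor. Section 3.3.6.5 calls the factor independently prognostic but gives no magnitude. A reader might also infer that the Day 1 value is never used. In fact it is the reference value for SRI-4, and section 6.3 summarises disease activity at baseline by arm, so an imbalance would be visible.

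**Conclusion.** The point holds as a modest improvement. In the documented primary and secondary SRI analyses, disease activity enters only as the screening split, while the endpoint is measured from Day 1. At odds ratios of 1.5 to 2.0 per SD the gain forgone is roughly one to one and a half power points. It reaches about three only at an odds ratio of 3.0 with a weak screening-to-Day 1 correlation, and it vanishes if the score carries no information. These sizes rest on the assumed odds ratios, correlations, median cut and linear log-odds effect, none of which the documents supply.

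Two stronger readings are not supported. One is that the primary comparison is biased or its error rate wrong; the simulated type I error stayed near 5%. The other is that the trial is underpowered on this account; the 88% is reached without any adjustment. Nor does the argument carry over to BICLA, which section 4.5.8.10 bases on BILAG improvement with only no worsening of SLEDAI-2K.

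**What to change.** Leave the randomisation strata and the CMH test as they are. Add to section 6.4.1, with detail in the Data Analysis Plan before unblinding, one supportive analysis: logistic regression with treatment, the stratification factors and Day 1 SLEDAI-2K as a continuous term. Average the predicted response over the trial population under each arm, and report the standardised difference in response rates with its 95% CI beside the CMH result. Apply it to SRI-4 at Weeks 24 and 48 and to SRI-6, and leave BICLA out.

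This takes a few lines of text and no new data. The downside is one additional model-based estimate to report and interpret. Specifying it in advance also avoids a post hoc argument should Day 1 scores turn out to differ between arms.

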### **3.3.6.6 Concomitant Medication Rationale**

Patients in this study will continue on their background SOC therapy in order to ensure that all patients receive effective therapy for SLE. GDC-0853 or placebo will be added to determine if GDC-0853 improves clinical response and/or reduces the need for systemic steroids in combination with SOC. The eligibility criteria exclude patients on certain SLE therapies in order to reduce the risk of participation in this study. Concomitant SLE therapies other than OCS will not be changed during the study (except in the event of toxicity), in order to reduce confounding effects on the safety and efficacy results of the study. OCS doses may be changed during certain time windows to minimize toxicity or for short-term treatment of increased SLE disease activity (see Section 4.3.2.3.3).

For guidance on concomitant medications that are unrelated to background SOC therapy, please refer to Section 4.4.

## **4. MATERIALS AND METHODS**

### **4.1 PATIENTS**

Approximately 240 patients with moderate to severe active SLE will be enrolled in this study.

#### **4.1.1 Inclusion Criteria**

Patients must meet all of the following criteria for study entry:

- Signed Informed Consent Form
- Age 18–75 years, inclusive
- Able to comply with the study protocol
- Fulfillment of SLE classification criteria according to either the current American College of Rheumatology (ACR) or Systemic Lupus International Collaborating Clinics (SLICC) criteria at any time prior to or at screening (see Appendix 5 and Appendix 6, respectively)
- At least one serologic marker of SLE at screening as follows:
  - Positive antinuclear antibody (ANA) test by immunofluorescent assay with titer  $\geq 1:80$ ; OR
  - Positive anti-double-stranded DNA (anti-dsDNA) antibodies; OR

- Positive anti-Smith antibody
- At both screening and Day 1, moderate to severe active SLE, defined as meeting all of the following unless indicated otherwise:
  - SLEDAI-2K score  $\geq 8$  (at screening only) with clinical SLEDAI-2K score  $\geq 4.0$  (at both screening and Day 1) (see [Appendix 10](#))
  - Physician’s Global Assessment  $\geq 1.0$  (out of 3) (see [Appendix 15](#))
  - Currently receiving at least one standard oral treatment (*e.g.*, corticosteroids, anti-malarials, and/or immunosuppressants) for SLE within the dose ranges, as specified below (see [Appendix 18](#)):
    - If on an OCS, the dose must be  $\leq 40$  mg/day prednisone (or equivalent, see [Appendix 18](#)) and must have been stable for at least 2 weeks prior to screening as well as during screening
    - If on anti-malarial or *immunosuppressant* therapies, may only be receiving medications from the following list within the specified dose range; dose and route of administration must be stable for 8 weeks prior to screening as well as during screening:
      - Azathioprine: 1 to 2.5 mg/kg/day
      - Methotrexate: 7.5 to 25 mg/week
      - Mycophenolate mofetil: 500 to 3000 mg/day
      - Mycophenolic sodium: 360 to 2160 mg/day
      - Hydroxychloroquine: 200 to 400 mg/day
      - Chloroquine: 100 to 250 mg/day
      - Quinacrine: 100 to 200 mg/day
      - Other: Consult with Medical Monitor

Note: Any combination of azathioprine, methotrexate, mycophenolate mofetil, or mycophenolic sodium is prohibited.

- For women of childbearing potential: agreement to remain abstinent (refrain from heterosexual intercourse) or use contraceptive methods listed in [Appendix 8](#) that result in a failure rate of  $< 1\%$  per year during the study treatment period and for a minimum of 60 days after the last dose of study drug or longer as required by local requirements for other standard of care medications. Women using estrogen-containing hormonal contraceptives as a method of contraception must also use a barrier.
  - A woman is considered to be of childbearing potential if she is postmenarcheal, has not reached a postmenopausal state ( $> 12$  continuous months of amenorrhea with no identified cause other than menopause), and has not undergone surgical sterilization (removal of ovaries and/or uterus).
  - Examples of contraceptive methods with a failure rate of  $< 1\%$  per year include bilateral tubal ligation, male sterilization, hormone-releasing intrauterine

devices, and copper intrauterine devices. Established proper use of hormonal contraceptives that inhibit ovulation also have a failure rate of < 1% per year; however, women using estrogen-containing hormonal contraceptives as a method of contraception must also use a barrier, such as a male condom, in conjunction with the hormonal contraceptives.

- The reliability of sexual abstinence should be evaluated in relation to the duration of the clinical trial and the preferred and usual lifestyle of the patient. Periodic abstinence (e.g., calendar, ovulation, symptothermal, or post-ovulation methods) and withdrawal are not acceptable methods of contraception.
- For men: agreement to remain abstinent (refrain from heterosexual intercourse) or use contraceptive measures, and agreement to refrain from donating sperm as defined below. Please also see [Appendix 8](#) for details:
  - Men with female partners of childbearing potential must remain abstinent or use a condom plus an additional contraceptive method that together result in a failure rate of < 1% per year during the treatment period and for at least 120 days (16 weeks) after the last dose of study treatment. Men must refrain from donating sperm during this same period.
  - Men with pregnant female partners must remain abstinent or use a condom during the treatment period and for at least 28 days after the last dose of study treatment to avoid exposing the embryo.
  - The reliability of sexual abstinence should be evaluated in relation to the duration of the clinical trial and the preferred and usual lifestyle of the patient. Periodic abstinence (e.g., calendar, ovulation, symptothermal, or post-ovulation methods) and withdrawal are not acceptable methods of contraception.

